5.4.3.5 Vital Signs

Summary statistics for observed and change from baseline values of each vital sign measurements, including blood pressure (Systolic/Diastolic) (mmHg), Pulse Rate (beats/minute) and temperature (°C) will be presented by placebo/ dose-level cohort and visit.

Vital signs will be summarized using the number of observations (n), Abnormal values (number of subjects with abnormal values), missing, mean, standard deviation (SD), median, Q1, Q3, minimum, and maximum along with the total number of subjects contributing values.

The decimal precision for each parameter will be based on the maximum number of decimals to which the results were reported on the eCRF.

All vital signs measurements will be listed. The listing will be sorted by placebo / dose-level cohort, subject, vital sign, visit and timepoint (if applicable).

The test status (Normal/Abnormal/ Not done) and the clinically significant abnormal values (Yes / No) will be shown.

5.4.3.6 12-Lead Electrocardiogram (ECG)

Summary statistics for observed and change from baseline values of each ECG parameter will be presented by placebo / dose-level cohort, and visit/timepoint. 12-lead ECG measurements will be conducted locally, including RR duration (sec), PR interval (ms), QRS duration (ms), QT duration (ms), QTcF (ms) and P wave duration (ms).

ECG will be summarized using the number of observations (n), Abnormal values (number of subjects with abnormal values), missing, mean, standard deviation (SD), median, Q1, Q3, minimum, and maximum along with the total number of subjects contributing values.

The decimal precision for each parameter will be based on the maximum number of decimals to which the results were reported on the eCRF.

All ECG measurements and overall interpretation results will be listed. The listing will be sorted by placebo/ dose-level cohort, Subject, parameter, visit and timepoint (if applicable).

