7. STUDY OBJECTIVES AND ENDPOINTS

Objective	Endpoint
Primary	
The primary objective of the study is to investigate the safety and tolerability of ATL-001 in healthy subjects	Incidence of adverse events (AEs) and of clinically relevant changes in vital signs values, electrocardiogram (ECG) data, physical examination and laboratory safety data for five different doses of ATL-001
Secondary	
To determine the PK of ATL-001 in healthy subjects	Derived pharmacokinetic parameters for ATL-001 including area under the plasma drug concentration versus time curve (AUC _(0-last) , AUC ₍₀₋₁₂₎ , AUC ₍₀₋₂₄₎), maximum observed plasma drug concentration (C _{max}), time to maximum observed plasma drug concentration (t _{max}), apparent terminal half-life (t _{1/2}), apparent total body clearance (CL/F) and apparent volume of distribution (Vz/F), as appropriate

Version: 4.0

Date: 13 December 2023

Sponsor: Atlas Molecular Pharma S.L. Study Code: ATL001-PI-CEP

NCT No.: 05647343

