11.4.4 Vital Signs

The following vital signs will be monitored as safety variables:

- Resting systolic and diastolic blood pressure (mmHg), after 5 minutes sitting
- Resting pulse rate (beats per minute), after 5 minutes sitting
- Axillary body temperature (°C)

Additional vital signs may be monitored for the safety of the subjects.

The observed values will be recorded and assessed as "normal" or "abnormal". Abnormal findings will be assessed as "clinically significant" or "not clinically significant".

The Investigator may choose to repeat any abnormal result once, in order to rule out measurement error. Clinically relevant deviations of vital signs results occurring during or at post-study examination must be reported and discussed with the Sponsor, if applicable. Repeated measurements are mandatory until their normalization or until the time course and reason of the underlying process can clearly be assessed positively.

The timing of the assessments is described in Section 8.2.1 and Table 1.

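### For vital signs and ECG, the SAP tabulates subjects with any abnormal value at each visit, not the incidence of clinically relevant change named in the primary endpoint

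*SAP*

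**What the plan says.** Protocol Section 7 gives the primary endpoint as "Incidence of adverse events (AEs) and of clinically relevant changes in vital signs values, electrocardiogram (ECG) data, physical examination and laboratory safety data", for five doses. It has two components, adverse events (AEs) and clinically relevant changes, and the second covers four domains.

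The raw material for the second component is collected. In Protocol 11.4.4, "The observed values will be recorded and assessed as" normal or abnormal, and abnormal findings are then classed as clinically significant or not. Protocol 11.4.5 has the same two-step assessment for ECG.

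The SAP uses only the first step in its tables:

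- **Vital signs (SAP 5.4.3.5).** The table has "Vital signs will be summarized using the number of observations (n), Abnormal values (number of subjects with abnormal values", plus the usual descriptive statistics. As to level, the measurements up to "temperature (°C) will be presented by placebo/ dose-level cohort and visit". The significance flag comes directly after the listing description: "The test status (Normal/Abnormal/ Not done) and the clinically significant abnormal values (Yes / No) will be shown". No count or percentage is attached to it.
- **ECG (SAP 5.4.3.6).** "ECG will be summarized using the number of observations (n), Abnormal values (number of subjects with abnormal values", and "each ECG parameter will be presented by placebo / dose-level cohort, and visit/timepoint". Clinical significance is not mentioned, and the overall interpretation is only listed.
- **All domains (SAP 5.4).** Unscheduled and repeat assessments go into listings and are kept out of summary tables.

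Protocol 13.1.4.2 has vital signs summarized by visit. It also says that the overall ECG interpretation, normal or abnormal, will be summarized.

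**The concern.** An incidence is the number of subjects affected over the period of observation, divided by the number at risk. For these two domains the SAP gives a prevalence of abnormal readings at each time point. A reader of the study report who wants to know how many subjects at a given dose had a clinically relevant vital-sign or ECG change would not find the answer in a table. The nearest number would be a count of something else.

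The study is descriptive and no test is affected. What is at stake is whether the main safety display matches the endpoint. If it does not, the choices on baseline abnormalities and repeats would be made by hand after the data are seen.

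**Working it through.** **1. Planned numbers.** SAP 5.1 gives five cohorts of 8: 5 × 8 = 40, which reproduces the stated total. With 6 active and 2 placebo per cohort (SAP 2.3.1), there are 6 active subjects per dose. Placebo is pooled (SAP 4.1), so 5 × 2 = 10.

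**2. Endpoint against table.**

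| Feature | Endpoint (Protocol 7) | SAP table (5.4.3.5, 5.4.3.6) |
|---|---|---|
| Finding counted | Clinically relevant | Any abnormal value |
| Relation to baseline | A change | None required for the count |
| Time frame | Incidence over the study | Each visit or time point separately |
| Readings used | Not restricted | Scheduled only (SAP 5.4) |

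On the second row, exclusion criterion 3 (Protocol 9.3) concerns clinically significant abnormalities. A subject with an abnormality judged not significant can enter and be counted at every visit.

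On the fourth row, Protocol 11.4.4 lets the investigator repeat an abnormal vital sign once to rule out measurement error, and requires repeats for clinically relevant deviations. Protocol 8.1.3 requires its QTcF criterion to be confirmed by repeated ECGs. The readings that settle relevance may therefore be among those left out of the tables.

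**3. Scheduled post-dose times.** From Protocol Table 1 and Section 8.2.1: Day 1 at 2 h, Day 2 at 24 h, Day 5 at 2 h, Day 6 at 24 h, FU-V1 and FU-V2. That makes six.

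**4. What by-visit counts can tell.** Let c₁ to c₆ be the counts at the six times and n the group size. The number of subjects ever affected lies between max(cₖ) and min(n, Σcₖ). With every cₖ = 1 and n = 6:

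- lower bound: max = 1, so 1/6 = 17%
- upper bound: min(6, 6) = 6, so 6/6 = 100%

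**5. Illustration under assumed rates.** The documents give no per-visit rate p. The any-visit proportion runs from p, if the same subjects are affected each time, to 1 − (1 − p)⁶, if visits are independent:

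| Assumed p | Full dependence | Independence |
|---|---|---|
| 2% | 2% | 11.4% |
| 5% | 5% | 26.5% |
| 10% | 10% | 46.9% |

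**6. What a subject-level display would show.** Exact (Clopper-Pearson) 95% intervals:

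| Subjects affected | Proportion | 95% CI |
|---|---|---|
| 0/6 | 0% | 0 to 45.9% |
| 1/6 | 16.7% | 0.4 to 64.1% |
| 2/6 | 33.3% | 4.3 to 77.7% |
| 0/10 (placebo) | 0% | 0 to 30.8% |
| 1/10 (placebo) | 10% | 0.3 to 44.5% |

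The estimate is imprecise, but it is the quantity the endpoint names.

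**7. The route through AEs.** Protocol 12.2 makes an asymptomatic laboratory or vital-sign abnormality an AE if it is clinically significant, and SAP 5.4.3.2 counts subjects with treatment-emergent AEs (TEAEs) across visits. Three limits remain:

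- a finding with symptoms is reported as the symptom
- the counts are spread over preferred terms, with no total for vital signs
- the paragraph on abnormal values names laboratory and vital signs, not ECG

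**8. ECG interpretation.** Protocol 13.1.4.2 promises a summary, and SAP 5.4.3.6 gives a listing. SAP 2.4 declares changes to the Screened population and the PK set only, so this reduction is not declared.

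**The case against.** The strongest reply is that the documents send these findings to the AE tables on purpose. Protocol 12.2 says that reporting an abnormality both as a finding and as an AE should be avoided. The AE definition in 12.1.1 covers any unfavorable sign. Section 12.2 also mentions abnormal diagnostic procedure results, which could reasonably take in ECG. On this view, a clinically significant asymptomatic vital-sign finding already gets a subject-level incidence. This stands in part for vital signs. For ECG it is an inference from general wording.

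Other replies also have force:

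- **Listings.** Vital-sign listings show the significance flag for each subject, and six subjects per dose can be counted by hand. That is true, but a hand count is not pre-specified.
- **Baseline.** Clinically significant abnormalities at screening are an exclusion, so the condition of being new would seldom remove anyone from a count of significant findings. It matters more for the count of abnormal values that the SAP now plans.
- **Overall summaries.** SAP 5.4 says that applicable data are summarized overall as well as by visit. It names no clinically significant count, and SAP 5.4.1.1 and 5.4.3.2 use the word for a column beside the cohorts.
- **Table shells.** SAP Section 7 refers to separate shells, which were not available. They may contain such a table, but the SAP text does not ask for one.

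A reader might infer that half of the primary endpoint goes unestimated. The documents do not support that. This point covers two of the four domains in the second component, the AE route recovers some vital-sign findings, and SAP 5.4.3.7 expressly sends clinically significant physical-examination findings to AEs, or to medical history if found at screening.

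**Conclusion.** The point holds for vital signs and ECG. The planned tables show a different quantity from the endpoint, and the AE tables narrow the gap without closing it. The gap is wider for ECG, where the SAP does not mention clinical significance and the protocol's interpretation summary has become a listing.

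The 17% to 100% range shows that by-visit counts do not determine a subject incidence. It applies to abnormal values as the SAP counts them and should not be read as the likely error. The rates in step 5 are assumptions.

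The conclusion rests on reading *clinically relevant change* as the investigator's *clinically significant* flag. Neither document makes that link, and this is itself something to settle. The change should be made, but it corrects a mismatch between endpoint and display and does not call the study's conduct into question.

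**What to change.** In SAP 5.4.3.5 and 5.4.3.6:

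1. State that the investigator's clinically significant flag defines a clinically relevant change.
2. Add, by dose and pooled placebo, the number (%) of subjects with at least one post-dose value recorded as abnormal and clinically significant that was not so at baseline.
3. Include unscheduled assessments, but not initial readings that a repeat under Protocol 11.4.4 showed to be measurement error. Write this as an explicit exception to the rule in SAP 5.4.
4. Label the table as the display for this component of the primary endpoint, and keep the by-visit tables as support.
5. Restore the summary of overall ECG interpretation, or declare its removal in SAP 2.4.

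The cost is one extra table per domain, a few sentences of SAP text, and some overlap with the TEAE tables, which a footnote can explain. No new data are needed, provided that the eCRF holds the flags the protocol requires for both domains.

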5.4.3.7 Physical Examination

All subjects will undergo a standard physical examination. General physical examinations will include the following body systems:

Heent, dermatological, psychiatric, neurological, cardiovascular, respiratory system, renal, abdominal and gastrointestinal, genitourinary, musculoskeletal, endocrine and metabolic, hematological and lymphatic, allergies and drug sensitivities, others.

The examinations will be recorded and assessed as “normal” or “abnormal”. Abnormal findings will be assessed as “clinically significant” or “not clinically significant”.

Any clinically significant abnormalities will be recorded either as medical history or concomitant disease (if detected at screening) or as adverse event.

Data from physical examinations will be listed. The listing will be sorted by placebo /dose-level cohort, subject, parameter, visit, and timepoint (if applicable).

5.4.4 Pharmacokinetic Analyses

Missing pre-dose ATL-001 concentration values will be imputed as 0. Other missing PK concentration values will be treated as missing for summary tables and figures. PK concentration values that are missing or not reportable will be reported in listing as missing or “NR”, respectively.

Plasma ATL001 concentrations that are below the lower limit of quantification (LLOQ) will be displayed as “<LLOQ” in data listings, and imputed as LLOQ/2 for summary tables and figures. LLOQ at pre-dose will be imputed as 0.

LLOQ values in the terminal phase and embedded LLOQ values (an LLOQ value between two quantifiable concentrations) will be set to missing for PK parameter calculation.

Plasma concentrations of ATL-001 will be summarized by ATL-001 dose group and nominal (scheduled) time point using descriptive statistics, including n, mean, SD, SE, minimum, maximum, median, coefficient of variation (CV%), geometric mean, and geometric CV%. Mean and individual concentration-time profiles will be presented graphically on linear and semi-log scales.

PK parameters will be summarized by ATL-001 dose group using descriptive statistics, including n, mean, SD, SE, minimum, maximum, median, coefficient of variation (CV%), geometric mean, and geometric CV%. Important PK parameters, e.g., AUC_{0-24} , AUC_{τ} , C_{max} and C_{max-ss} will be graphically presented using box plot.

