8.2.1.2.2 Hospital admission (Day 5 to Day 6)

8.2.1.2.2.1 Day 5

At Day 5, the following activities and assessments will be performed prior to IMP administration:

- Urine pregnancy test (for female subjects of childbearing potential only)
- PK blood sampling (0 min or pre-dose)

After performing all the previous assessments, the IMP will be administered, and the subjects will remain in the hospital for 24 hours. During Day 5, the following activities and assessments will be performed after IMP administration:

- Physical examination (2 hours after the last IMP dose)
- Vital signs, including blood pressure, pulse rate and body temperature (2 hours after the last IMP dose)

Version: 4.0

Date: 13 December 2023

Sponsor: Atlas Molecular Pharma S.L. Study Code: ATL001-PI-CEP

NCT No.: 05647343

• Laboratory safety assessments, including hematology, biochemistry and urinalysis (2 hours after the last IMP dose)

- ECG (2 hours after the last IMP dose)
- PK blood sampling (15 min, 30 min, 1 hour, 1:30 hours, 2 hours, 2:30 hours, 3 hours, 4 hours, 6 hours, 8 hours and 12 hours after the last IMP dose)
- Concomitant medications
- AEs

8.2.1.2.2.2 Day 6

Subjects will be discharged at Day 6 after completing their assessments. At Day 6 (24 hours after the last IMP dose), the following activities and assessments will be performed:

- Physical examination
- Vital signs, including blood pressure, pulse rate and body temperature
- Laboratory safety assessments, including hematology, biochemistry and urinalysis
- ECG
- PK blood sampling
- · Concomitant medications
- AEs

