2.3.2 Study treatment

The product name is referred to as ATL-001. ATL-001, ciclopirox olamine oral solution, 20 mg/ml is a new oral formulation of ciclopirox. On the morning of Day 1 to Day 5, each subject will receive a single oral dose of ATL-001 or placebo (i.e., total of 5 administrations of IMP) administered under fasting conditions (overnight fast; at least 10 hours) following the instructions below:

| Cohort | Investigational medicinal product | Route | Administration Days |
|--------|-----------------------------------|-------|---------------------|
| 1 | ATL-001 0.2 mg/kg / Placebo | Oral | 1, 2, 3, 4, 5 |
| 2 | ATL-001 0.5 mg/kg / Placebo | Oral | 1, 2, 3, 4, 5 |
| 3 | ATL-001 1 mg/kg / Placebo | Oral | 1, 2, 3, 4, 5 |
| 4 | ATL-001 2 mg/kg / Placebo | Oral | 1, 2, 3, 4, 5 |
| 5 | ATL-001 4 mg/kg / Placebo | Oral | 1, 2, 3, 4, 5 |

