⁴ Laboratory safety assessments include: hematology, biochemistry, and urinalysis

⁵ Viral serology will comprise human immunodeficiency virus (HIV) I and II, hepatitis B virus surface antigen (HBsAg) and hepatitis C virus testing, and coronavirus disease (COVID)-19 testing by polymerase chain reaction (PCR)

⁶ Pregnancy testing of female subjects only. At screening pregnancy test will be done with using the blood sample; urine pregnancy test will be done on admission.

⁷ Also pre-dose at Day 5

⁸ Adverse events will be daily recorded by the subject in the subject diary and will not involve visit to the hospital.

⁹ Pre-treatment-emergent events.

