5.4.8 Handling of Missing Data

No missing value imputation will be done. All analyses will be conducted on observed data.

Only will be considered the imputation to classify the adverse events into TEAE or non TEAE. For this purpose, is strictly necessary the start date of the event so if it is missing, imputation will be performed following the next rules:

- If only the day is missing, 1st of the registered month will be interpreted.
- If both day and month are missing, it will be placed 1st of January of 2023

Although this option is being contemplated, it is not expected to occur.

Just in case the previous imputation generated an incoherence considering the rest of dates reported for any subject, the day imputed would be the corresponding day according to the rest of dates for the same subject.

Also, if there is any partial date and it has relation with the medication, it will be considered TEAE.

These data imputations are for analysis purpose only and will not be used in listings.

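### The SAP sets a missing pre-dose concentration to 0 without limiting the rule to Day 1, so a lost Day 5 trough sample is summarised as zero drug

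*SAP*

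**What the plan says.** - **Missing samples.** SAP 5.4.4: "Missing pre-dose ATL-001 concentration values will be imputed as 0". All other missing concentrations stay missing in tables and figures.
- **Below-LLOQ samples.** SAP 5.4.4: post-dose values are "imputed as LLOQ/2 for summary tables and figures", but "LLOQ at pre-dose will be imputed as 0". For parameters, terminal and embedded below-LLOQ values "will be set to missing for PK parameter calculation".
- **When pre-dose samples are taken.** Before the Day 1 dose and, by footnote 7 of the schedule in SAP 2.3.5, "Also pre-dose at Day 5". Protocol 8.2.1.2.2 lists the same Day 5 sample.
- **Dosing.** SAP 2.3.2: "On the morning of Day 1 to Day 5, each subject will receive a single oral dose of ATL-001 or placebo". Four doses therefore precede the Day 5 pre-dose sample.
- **General rule.** SAP 5.4.8: "No missing value imputation will be done. All analyses will be conducted on observed data". The only exception it then gives is for adverse event onset dates. SAP 5.4 permits no exceptions beyond those in 5.4.8.
- **Parameters.** SAP 4.6 lists Cmin-ss for Day 5 without saying which samples it is taken from.
- **Protocol.** Section 13.1.5.1 sets below-LOQ concentrations to zero both in summaries and in parameter calculation, and does not report a geometric mean when zeros are present. It has no rule that turns a missing sample into zero.

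**The concern.** Before the first dose, zero is known to be right. Before the fifth dose it is not: the sample then measures what remains of four doses. A tube lost on Day 5 carries no information about that amount, yet the rule records it as absence of drug. No other section of the SAP or protocol limits the rule to Day 1.

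At stake is the Day 5 trough summary and, depending on its definition, Cmin-ss. With six active subjects per dose group, one artificial zero visibly changes the mean and CV and removes the geometric statistics that SAP 5.4.4 plans.

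**Working it through.** The documents state no figure on this point, so there is none to reproduce. The check is of the text first, then of size.

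**1. Text.** The zero rule in 5.4.4 applies to pre-dose values. Pre-dose values exist on Day 1 and Day 5. No restriction by day appears, so following the rule sets a missing Day 5 value to 0. Because 5.4 admits only the exceptions in 5.4.8, and 5.4.8 covers only onset dates, the SAP contradicts itself here. SAP 2.4, which lists changes from the protocol, does not mention the new rule.

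**2. Effect on a cohort summary.** Input: 6 active subjects per cohort (SAP 2.3.1). Take six equal troughs of 1 and set one to 0.

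- Mean = 5/6 = 0.833, a fall of 16.7%.
- SD = √{[5 × (1/6)² + (5/6)²]/5} = √(1/6) = 0.408, so CV = 0.408/0.833 = 49%, where the true CV is 0.
- With two zeros the mean falls by 33.3% and the CV is 77%.
- The logarithm of 0 is undefined, so the geometric mean and geometric CV cannot be computed with any zero present.

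**3. How large the lost trough could be.** Inputs: once-daily dosing, five doses, the SAP 4.6 sampling times, and a half-life below 6 h, which Protocol 6.2.2 quotes for an earlier oral formulation. Assumed: one-compartment kinetics, absorption half-life 0.5 h (ka = ln 2/0.5 = 1.386 per h), and half-lives of 2 to 8 h to show the range. One dose gives C(t) = ka/(ka − ke) × [exp(−ke·t) − exp(−ka·t)] with ke = ln 2/half-life. The Day 5 profile is the sum of C(t + 24k) for k = 0 to 4, and AUCtau is by linear trapezoid.

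| Half-life (h) | Day 5 pre-dose as share of Cmax-ss | Change in AUCtau if set to 0 | Change in Cmax-ss |
|---|---|---|---|
| 2 | 0.05% | −0.001% | 0 |
| 3 | 0.7% | −0.013% | 0 |
| 4 | 2.4% | −0.04% | 0 |
| 6 | 8.5% | −0.10% | 0 |
| 8 | 15.9% | −0.16% | 0 |

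With ka of 1 and 2 per h instead, the trough share is 9.3% and 7.9% at 6 h, 2.7% and 2.2% at 4 h, and 0.8% and 0.6% at 3 h.

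**4. Accumulation ratios.** SAP 4.6 defines them as AUCtau/AUC0-24 and Cmax-ss/Cmax. The first moves by the AUCtau percentage above and the second not at all.

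**5. How often.** The documents give no rate of missing samples. If 5% to 10% of Day 5 pre-dose samples were missing (an assumption), the chance of at least one among 6 is 1 − 0.95⁶ = 26% to 1 − 0.90⁶ = 47%. Among all 30 active subjects (5 × 6) it is 79% to 96%.

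**6. Below-LLOQ values.** Suppose every subject is below LLOQ both before the Day 5 dose and 24 h after it. The tables would show 0 at the first time and LLOQ/2 at the second, a difference created by the label alone. The protocol rule would give 0 at both.

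**The case against.** **Accumulation.** A reader might infer that a lost trough becomes evidence of no accumulation. The documents do not support that: neither planned ratio uses Cmin, and both are practically unchanged. Nor is Cmin-ss among the protocol's PK parameters (sections 7 and 11.2.3) or among those the SAP names for box plots.

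**Cmin-ss.** A reader might also infer that Cmin-ss is necessarily forced to 0. That requires the imputed value to enter parameter calculation and Cmin-ss to include the 0 h sample. The SAP states neither and excludes neither. The protocol also refers to a PK analysis plan, and the SAP to separate PK table shells, either of which might settle it.

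**Below-LLOQ troughs.** It is tempting to call zero an outright error here too. It is not: zero is the protocol's own rule, and the error cannot exceed the LLOQ. What stands is that the SAP treats comparable 24 h samples differently.

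**Geometric mean.** The protocol foresees zeros by suppressing the geometric mean. That avoids an undefined result, but the dose group still loses a planned statistic because of a value nobody measured.

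**Size.** The 6 h half-life is an upper bound from another formulation, and at 3 h the trough is below 1% of Cmax. The Day 5 sample is also drawn on site, which may keep losses few. Both limit the likely effect. Neither makes zero the right entry for a lost sample.

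**Conclusion.** The point holds in a limited form. Applied literally, SAP 5.4.4 replaces a missing Day 5 trough with zero and conflicts with SAP 5.4 and 5.4.8. One such value in a group of six lowers an otherwise equal mean by 16.7%, produces a CV of 49% and removes the geometric summaries.

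The trough being replaced is under 1% of Cmax at a 3 h half-life and about 8–9% at 6 h, given the assumed model and absorption rate. The Cmin-ss part depends on a definition that the SAP leaves open. Quantified troughs are untouched, and AUCtau, Cmax-ss and the accumulation ratios are essentially unaffected. How often the rule would act cannot be computed, because the documents give neither the LLOQ nor a missing rate.

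This should be corrected, but it does not threaten the primary safety objective or the main exposure results.

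**What to change.** 1. In SAP 5.4.4, limit the missing-to-zero rule to the Day 1 pre-dose sample. Treat a missing Day 5 pre-dose value as missing in summaries and for Cmin-ss.
2. List the Day 1 exception in 5.4.8 so that 5.4, 5.4.4 and 5.4.8 agree.
3. Define Cmin-ss by the samples it uses. State what time-0 value AUCtau takes when the Day 5 pre-dose sample is missing. Any substitute, such as the 24 h value, is itself an imputation and should be declared, although it matters little numerically.
4. As a secondary point, apply one stated below-LLOQ rule in summaries to Day 5 pre-dose and 24 h post-dose samples. Reconcile it with Protocol 13.1.5.1 and record any departure in SAP 2.4.
5. State the parameter rule for a below-LLOQ Day 5 pre-dose value, which as a first sample is neither terminal nor embedded. Do not set a below-LLOQ trough to missing for Cmin-ss. If the 24 h value were also dropped, the minimum could become the 12 h value, which under log-linear decline is 2^(12/4) = 8 times the 24 h level at a 4 h half-life and 2^(12/3) = 16 times at 3 h.

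The main correction costs one sentence in 5.4.4 and one line in 5.4.8. The rest is a few lines of definition. No new data are needed.
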